Indications for Use/Intended Use	The MIRI-TL is a purpose built embryo culture incubator using a built-in microscope and camera designed specifically for the continuous assessment of embryo development in-vitro . As images are digitally obtained and stored, a video can be generated to enable more objective and reliable grading criteria. This technology, in conjunction with the MIRI-TL Viewer allows for non-invasive viability evaluation and assessment allowing for better prediction of embryo developmental potential and implantation success. The MIRI-TL is CE marked for clinical use. The CultureCoin is intended to be used to hold human oocytes and embryos during handling and culture.
Study Purpose	The purpose of this study is to demonstrate and validate the non-inferior or superior safety and efficacy of the MIRI-TL compared to standard big-box incubators used for embryo culture.
Study Design	Prospective, observational, randomized, double-arm

Safety Measures	Adverse events and device malfunctions will be reported and summarized from the start of embryo culture through study exit.
------------------------	---

Number of Subjects	Up to 500 patients
Subject Population	Patients undergoing in vitro fertilization treatment who fulfill all eligibility criteria.
Eligibility Criteria	
Inclusion Criteria:
 
 • At least 18 years of age • Women undergoing in vitro fertilization treatment using their own or frozen oocytes • Fresh or Frozen Embryo Transfer • Fertilization by ICSI • At least 4 diploid (2PN) embryos at fertilization check • Willing to have all inseminated oocytes imaged by Miri • Willing to comply with study protocol and procedures • Willing to provide written informed consent 
Exclusion Criteria:
 
 • Fertilization using surgically removed sperm • History of cancer
Number of Sites	1
Study Duration	Expected study duration is 18 months including enrollment and follow-up. Subjects will be followed until pregnancy outcome has been determined (i.e. date of negative hCG test, 8-12 week clinical pregnancy ultrasound, or date of live birth, if pregnant).
Summary of Data Collection	
 • Enrollment: Demographics, IVF and pregnancy history • IVF Lab: Embryo morphology • Time-Lapse Imaging Data • Pregnancy test and Live Birth Outcome • Preimplantation Genetic Screening (PGS) Data, if applicable • Frozen Embryo Transfer (FET) Data, if applicable
Study Start	April 2016

1. Introduction

The purpose of this clinical study protocol is to gather information regarding the performance and safety of a novel time lapse incubator compared to standard incubator systems. The MIRI-TL and the Culture Coin are CE Marked and have therefore fulfilled EU safety and performance criteria. In the US, 510(k) submission for both products is planned for Q2/Q3 2016.

As the sponsor of this clinical study, ESCO Medical has the overall responsibility for the conduct of the study, including assurance that the study will be performed according to the clinical investigation plan, applicable US Food and Drug Administration (FDA) and local regulation.

2. Background

The optimal goal of IVF should be the delivery of a healthy singleton baby and healthcare providers may be compelled via legal, financial, and moral obligations to reduce multiple pregnancies.¹⁻⁴ The clinical dilemma is how to restrict the number of embryos for transfer to prevent multiple births while at the same time maintaining or improving IVF success rates. The ability to selecting the highest quality embryo that is most likely to result in implantation becomes the key solution, however, this has proven to be challenging.

In the late 1990s, improved culture media enabled blastocyst culture, allowing embryos to develop in a petri dish for 2 to 3 additional days. Generally, about 40% of the embryos will form a blastocyst while others arrest in the culture dish during this extended period of incubation. It was broadly reported that blastocyst formation was a key embryo selection criterion for predicting successful implantation. Papanikolaou et al demonstrated in prospective randomized studies that embryo implantation rates and live birth rates were significantly improved with Day 5 transfer, as compared to Day 3 transfer.⁵⁻⁶ Because of improved implantation and live birth rates, blastocyst culture was widely adopted in clinics, in particular those which utilized single embryo transfer.

Embryos selection based on traditional morphology scores developed in the early 1980s. The morphological criteria are based on multiple 'static' observations of embryos under regular light microscopes. This involved removing the culture dish, which contained the embryos, from the incubator on a daily basis and assessing the embryos based on their morphology and growth. A number of studies have reported observations relating embryo morphology and implantation, including 2-pronuclear score, early cleavage observation, Day 2 or

Day 3 cleaved embryo assessments, and Day 5 or Day 6 blastocyst grading.⁷⁻²⁴

However, despite exhaustive efforts by clinical embryologists using a regular light microscope to assess embryo quality, it is clear that traditional morphology grading, which only captures static images at a few time points, is of limited predictive value.

Several studies have indicated that using information obtained from time-lapse imaging, which provides a continuous 'movie' of embryo development, may improve embryo selection and ultimately improve clinical pregnancy or implantation.²⁵⁻²⁷ This is partly due to the non-invasive and controlled micro environment most purpose built time-lapse incubators provide. The literature has been encouraging as it appears that using time-lapse in the IVF laboratory may have a significant positive impact by providing embryologists with an additional tool to assess and predict which embryo is more likely to lead to a successful pregnancy.

3. Study Objectives

The purpose of this clinical study is to demonstrate and validate the safety and efficacy of the purpose built MIRI-TL incubator and correlate morphokinetic data to improved success rates.

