Embryos with incomplete annotations will be excluded from analysis. All variables will be tested for normality using Shapiro–Wilks test. Continuous data following a normal distribution will be analyzed with Students t-test.

Continuous data not fulfilling the assumption of normality will be analyzed with non-parametric tests such as the Wilcoxon rank-sum test. For categorical data Chi-squared or Fisher's exact test will be used. Two-tailed p-values < 0.05 will be considered significant.

8. Study Protocol

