8.0 Patient Randomization

Patients will be randomized to the MIRI-TL group (MIRI) or the Standard culture group (SC) by randomization number generator through www.randomizer.org, using a number set from 1 to 500. Numbers 1-300 will be assigned to the study (MIRI-TL) group while numbers 301-500 will be assigned to the control (Standard Incubator).

8.1 Egg Retrieval and Fertilization-Day 0

Egg retrieval and fertilization follow the standard protocol in place at the clinical site. Insemination, by intracytoplasmic sperm injection (ICSI) will take place on Day 0 (egg retrieval day) following standard protocol currently in place at the clinical site. The fertilized eggs should be free of cumulus cells as much as possible. If the cumulus cells remain in place, they may interfere with the quality of the imaging. Immediately after micro insemination, eggs will be placed in individual wells within a CultureCoin (MIRI group), or a standard culture dish (SC group), and incubated in the MIRI-TL or standard incubator respectively. All eggs will be cultured in the standard fertilization media currently in place at the clinical site. At 20hr after insemination, the MIRI-TL imaging software will be Paused, and all embryos will be examined by the embryologist for successful fertilization (2PN). All normally fertilized eggs will be placed into a new CultureCoin (MIRI group) or standard culture dish (SC group) containing the standard embryo culture media, and incubated in the MIRI-TL or standard incubator respectively.

Once an embryo is assigned a micro-well location, it must remain in the same location throughout the study imaging period. Embryos assigned to the MIRI group will be imaged in the CultureCoin from Day 0 to Day 7. Images of the developing embryos will automatically be captured with the MIRI-TL Microscope. Data collected will include the following:

- Number of eggs inseminated

- Fertilization method
- Total number of fertilized eggs (2PN)

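### The entry criterion of at least 4 2PN embryos is read about 20 h after arm-specific culture starts, and no as-randomised analysis set says what happens to randomised patients who fail it

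*Combined protocol and SAP*

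**What the plan says.** The synopsis lists "At least 4 diploid (2PN) embryos at fertilization check" among the inclusion criteria and describes the subject population as "Patients undergoing in vitro fertilization treatment who fulfill all eligibility criteria". Its study purpose is to "demonstrate and validate the non-inferior or superior safety and efficacy of the MIRI-TL compared to standard big-box incubators used for embryo culture".

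Section 8.0 gives the method of allocation: "Patients will be randomized to the MIRI-TL group (MIRI) or the Standard culture group (SC) by randomization number generator". It does not say when the number is drawn. Section 8.1 then says: "Immediately after micro insemination, eggs will be placed in individual wells within a CultureCoin (MIRI group), or a standard culture dish (SC group"). At 20 h after insemination, "all embryos will be examined by the embryologist for successful fertilization (2PN"). The data listed in section 8.1 include "Number of eggs inseminated" and the total of 2PN eggs.

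Section 7 bases the between-arm sample size on blastocysts as a share of inseminated oocytes: 25% assumed, a 20% increase to be detected, 1300 oocytes (about 163 patients) per group. It defines no patient-level analysis set. The only exclusion it states is at embryo level: "Embryos with incomplete annotations will be excluded from analysis". Section 8.13 says that subject data enter the analyses up to withdrawal of consent or termination of the study; it does not mention a patient found ineligible after allocation.

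**The concern.** Eggs cannot go into arm-specific dishes unless the arm is known, so allocation must come before the 2PN check even though section 8.0 gives no time. The 2PN count is then a post-randomisation measurement, taken after about 20 h in the assigned culture system.

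The powered quantity has inseminated oocytes as its denominator, so fertilisation is one of its factors. If patients with fewer than 4 2PN are dropped, the analysis selects on a component of the outcome. Were one system to lower fertilisation, it would lose more of its worst patients and the loss would look smaller than it is. A benefit would be understated in the same way. For a purpose that includes non-inferiority, shrinkage of a true loss is the unsafe direction.

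**Working it through.** **1. The plan's own figure.** For 25% vs 30%, two-sided 0.05, 80% power, the usual two-proportion formula gives 1251 oocytes per group, or 1291 with continuity correction; the plan states 1300. Reading the 20% as absolute (25% vs 45%) gives 89, so the increase is relative and the target is 5 points. Oocytes per patient: 1300/163 = 7.98. The standard error of the difference, with independent oocytes, is sqrt(2 × 0.25 × 0.75/1300) = 0.0170, or 1.7 points.

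**2. Inputs for the illustration.** The documents give no fertilisation rate, no spread of oocyte counts and no within-patient correlation. Assumed:
- blastocysts per 2PN, b = 0.40 (section 2 gives about 40% of embryos, without naming 2PN as the denominator);
- fertilisation 62.5% as the base, since 0.625 × 0.40 = 0.25 is the plan's rate; 70% as an alternative;
- 8 or 12 oocytes in every patient, or Poisson with mean 8;
- within-patient correlation 0 (binomial) or 0.1 (beta-binomial).

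**3. Formula.** With X the number of 2PN from n oocytes at fertilisation rate f, the rate over all randomised patients is b × f. The rate over retained patients is b × E[X; X ≥ 4] / (n × P(X ≥ 4)), pooled over n when n varies.

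Example, n = 8, f = 0.625, correlation 0:
- P(X ≤ 3) = 0.0004 + 0.0052 + 0.0304 + 0.1014 = 0.1374.
- E[X; X ≥ 4] = 5 − (0.0052 + 0.0608 + 0.3042) = 4.6298.
- Retained rate = 0.40 × 4.6298/(8 × 0.8626) = 0.2684.
- At f = 0.55 the retained rate is 0.2520, so the visible difference is −0.0164.
- The true difference is 0.40 × (0.55 − 0.625) = −0.0300.

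**4. Results, in percentage points (correlation 0 / 0.1).**

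| Fertilisation | True loss | 8 oocytes | 12 oocytes | Poisson, mean 8 |
|---|---|---|---|---|
| 62.5% to 55% | 3.0 | 1.64 / 1.44 | 2.68 / 2.19 | 2.26 / 1.88 |
| 70% to 68% | 0.8 | 0.58 / 0.48 | 0.78 / 0.68 | 0.66 / 0.57 |
| 62.5% to 60.5% | 0.8 | 0.47 / 0.41 | 0.74 / 0.61 | 0.62 / 0.52 |
| no difference | 0 | 0 | 0 | 0 |

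Hidden part: for the large fall, 3.0 − 2.68 = 0.3 up to 3.0 − 1.44 = 1.6 points. For a 2-point fall, 0.8 − 0.78 = about 0 up to 0.8 − 0.41 = 0.4 points.

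Patients below 4 2PN at 62.5% fertilisation: 14% / 21% with 8 oocytes, 1% / 6% with 12, about 26.5% / 30% with Poisson mean 8.

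**5. Sensitivity.**
- The planning average of 8 may already describe eligible patients. Setting the Poisson mean to 6.71 / 6.85, so that retained patients average 8 oocytes at 62.5% fertilisation, makes the large fall show as 2.1 / 1.7 points. That lies inside the range above, although about 40% of patients would then fall below 4 2PN.
- With negative-binomial oocyte counts (mean 8, SD 4), fertilisation 70% vs 60% and b = 0.25/0.70, a true loss of 3.6 points shows as 3.0; 27% and 36% of patients are lost.

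The direction is the same throughout: the difference shrinks toward zero.

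**The case against.** A reader might infer that the plan removes randomised patients with low 2PN counts by rule. It does not say so. Section 7 excludes only embryos with incomplete annotations; section 8.1 moves every normally fertilised egg on, with no threshold of 4; the exit reasons in section 8.13 do not name 2PN failure, though that list is open-ended and has an 'other' entry. The sentence in 8.13 on including subject data could even be read as keeping these patients. This stands: exclusion is an inference from the criterion and the population line. But the 8.13 sentence concerns withdrawal and termination, so it does not settle the matter.

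A reader might also infer that the comparison is biased, or that the device impairs fertilisation. The documents support neither. Both arms use the same fertilisation medium, no passage says that early culture changes fertilisation, and with equal rates nothing is hidden.

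The size also rests on assumed inputs. The largest hidden loss needs a 7.5-point fall, exactly 8 oocytes in every patient and correlation 0.1. A 2-point fall hides at most 0.4 points, well under the 1.7-point standard error.

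Finally, the primary objective in section 3.1 is data collection, no primary endpoint is named, and the comparison of time to start of blastulation by ploidy is within the MIRI-TL group and so gains no between-arm bias from this criterion. That is fair, but the synopsis purpose is comparative and section 7 powers a between-arm difference.

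**Conclusion.** The gap in the text is certain. An inclusion criterion is read after allocation and after about 20 h of the compared intervention, and the plan does not say how randomised patients who fail it are analysed.

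The consequence is conditional on two things: that the synopsis population is applied to the analysis, and that early culture changes fertilisation. If either fails, there is no between-arm bias from this source. If both hold, 0.3 to 1.6 points of a 3.0-point loss would be hidden under the assumptions shown, and about 0 to 0.4 of a 0.8-point loss, against a planned target of 5 points. Between 1% and 30% of patients would fall below the threshold at 62.5% fertilisation under the same main assumptions.

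It should be fixed, because a study that compares culture systems should not have to assume that the first 20 h have no effect. Confidence is medium, since the magnitude is illustrative. The sample-size figure itself is not in error.

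**What to change.** - In section 7, define the main between-arm comparison as all randomised patients with at least one injected oocyte, in the arm assigned, on blastocysts per inseminated oocyte.
- Reword the synopsis criterion and the subject-population line so that at least 4 2PN defines a sensitivity subset and does not remove a randomised patient from the main analysis.
- In section 8.0, state when the randomisation number is drawn relative to ICSI.
- Report the number of patients below 4 2PN by arm.

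The cost is two reworded synopsis lines, one analysis-set paragraph and one sentence on timing. Eggs inseminated and 2PN counts are already recorded under section 8.1, so the by-arm report needs no new data. Laboratory outcomes must, however, be recorded for patients who would otherwise leave the study. The main analysis would also describe a wider population than the present criterion, because patients with low fertilisation stay in it.

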3.1 Primary Objective

- To collect safety and imaging data on the MIRI-TL and CultureCoin.

3.2 Secondary Objectives

- To collect enrollment data: demographics, IVF and pregnancy history
- To collect Day 3, Day 5 and Day 6 embryo morphology data
- To collect pregnancy test and live birth outcome data
- To collect pre-implantation genetic screening (PGS) data (if applicable)
- To collect Frozen Embryo Transfer (FET) data (if applicable)

4. Description of Device

The Miri- TL, manufactured by the study sponsor Esco Medical is a closed-system incubator device with built-in visual monitoring system. This closed system incubation system eliminates any environmental disruption and contamination risk by daily handling. The built-in camera has the ability to record cell division kinetics and morphology of developing embryos which can provide more reliable indicators of embryo quality. This novel time-lapse incubator captures images at five (5) minute intervals and its six (6) separate incubation chambers maximizes temperature and gas stability, providing a safe and secure environment for human embryos.

Figure 1: MIRI-TL

4.1 CultureCoin

The 16-well CultureCoin (**Figure 2**) is a standard size (60mm) embryo culture dish with individual micro-wells aligned in a row in the center of the dish. Each micro-well is designed to accommodate a single patient's oocytes or developing embryos through the blastocyst stage and are culture individually. The 16-well CultureCoin is designed to fit in only one (1) position in one (1) of the individual six (6) incubator chambers, and each micro-well is identified to facilitate embryo tracking (for example, micro-well

Figure 2: CultureCoin

5. Number of Centers and Study Duration

The TiMMI study will include only one investigational site. This site will conduct the study under a single clinical investigation plan.

Expected study duration is 18 months including enrollment and follow-up. Subjects will be followed until pregnancy outcome has been determined (i.e. date of negative hCG test or 8-12 week clinical pregnancy ultrasound, if pregnant).

6. Study Design

This is a prospective, non-blinded, observational, randomized, double-arm study.

7. Statistical Methods and Analyses

Up to 500 subjects' embryos will be collected in this ongoing data collection protocol. We aim to recruit 200 patients in the standard culture group, and 300 patients in the MIRI-TL group.

Assuming that 25% of all inseminated oocytes would develop into blastocysts (based on published clinical data), at least 1300 inseminated oocytes (~163 patients) would be needed in each group to detect an increase in blastocyst proportion of 20% with 80% power and a significance level of 0.05 (two-tailed tests).

Assuming that time from insemination to start of blastulation (tSB) follows a normal distribution, and is 96h with a variance of 49h in euploid embryos, and 98h (variance 49h) in aneuploid embryos, ~405 blastocysts (1620 inseminated oocytes = 203 patients) in the MIRI-TL group will need to be biopsied to detect a significant difference in tSB (80% power, 0.95 confidence level, 2-tailed test). Since ~80% of all patients receive PGS at our clinical site, we will need ~255 patients in our MIRI-TL group.

To account for patient dropout and lower than expected oocyte retrieval per patient, we propose to recruit up to 500 subjects in this ongoing data collection protocol: 200 patients in the standard culture (SC) group and 300 patients in the MIRI-TL (MIRI) group.

Embryos with incomplete annotations will be excluded from analysis. All variables will be tested for normality using Shapiro–Wilks test. Continuous data following a normal distribution will be analyzed with Students t-test.

Continuous data not fulfilling the assumption of normality will be analyzed with non-parametric tests such as the Wilcoxon rank-sum test. For categorical data Chi-squared or Fisher's exact test will be used. Two-tailed p-values < 0.05 will be considered significant.

8. Study Protocol

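### Patients are randomised, but the blastocyst comparison is sized on independent oocytes and no unit of analysis is named; an oocyte-level test would exceed its 5% error rate

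*Combined protocol and SAP*

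**What the plan says.** Section 8.0 makes the patient the unit of randomisation: "Patients will be randomized to the MIRI-TL group (MIRI) or the Standard culture group (SC"). Section 8.1 places the patient's injected eggs in the dish and incubator of her arm. The eligibility criteria in the synopsis require "At least 4 diploid (2PN) embryos at fertilization check", so every eligible patient contributes several oocytes.

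Section 7 assumes that 25% of inseminated oocytes become blastocysts and states that "at least 1300 inseminated oocytes (~163 patients) would be needed in each group to detect an increase in blastocyst proportion of 20" per cent, with 80% power and a two-sided 0.05 level. It then plans "200 patients in the standard culture (SC) group and 300 patients in the MIRI-TL (MIRI) group". The reason given for the larger numbers is "To account for patient dropout and lower than expected oocyte retrieval per patient"; correlation within patients is not mentioned.

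The test rules in Section 7 are generic. For continuous data, "Continuous data following a normal distribution will be analyzed with Students t-test", with the Wilcoxon rank-sum test otherwise. "For categorical data Chi-squared or" Fisher's exact test is the rule for categorical data. No unit of analysis, patient-level summary or cluster-adjusted method is named.

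**The concern.** Oocytes from one patient share her age, her stimulation cycle and usually the same sperm source, so their outcomes are likely to be correlated. Arm does not vary within a patient. A test that counts oocytes as independent therefore understates the variance of the difference between arms, and its false-positive rate rises above the nominal level. Recruiting more patients does not cure this.

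Whether an oocyte becomes a blastocyst is a categorical outcome, and Section 7 uses oocytes as the denominator. The natural reading is thus an oocyte-level Chi-squared or Fisher test, although the plan does not say so outright. The same independence assumption sits in the sample-size sentence.

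The stake is the comparative claim. The synopsis gives the purpose as to "demonstrate and validate the non-inferior or superior safety and efficacy of the MIRI-TL compared to standard big-box incubators used for embryo culture", and this is the only between-arm comparison with a calculated size. The other calculation, for time to start of blastulation, compares euploid with aneuploid embryos inside the MIRI-TL group and is outside this point.

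**Working it through.** **Inputs from Section 7.** Control proportion 0.25; 20% increase; 80% power; two-sided 0.05; 1300 oocytes and about 163 patients per group, so 1300/163 = 7.98, about 8 oocytes per patient; 200 and 300 patients planned.

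**Assumed.** The documents give no ICC. I use 0.02, 0.05, 0.10 and 0.20, with 8 oocytes for every patient unless stated.

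**1. Reproducing the 1300.** Read as a relative increase, the comparison is 0.25 against 0.30, with mean 0.275.

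n = [1.960·√(2·0.275·0.725) + 0.842·√(0.25·0.75 + 0.30·0.70)]² / 0.05² = (1.2377 + 0.5306)² / 0.0025 = 1250.7

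With continuity correction this becomes 1290.4, within 1% of 1300. An absolute increase (25% to 45%) would need fewer than 100 oocytes per group, so the relative reading is secure. The formula treats oocytes as independent; patients enter only as a divisor.

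**2. Design effect.** DE = 1 + (8 − 1)·ICC.

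**3. True error rate of an oocyte-level test.** For the uncorrected Chi-squared test, alpha = 2·[1 − Φ(1.96/√DE)]. At ICC 0.05, DE = 1.35, 1.96/√1.35 = 1.687 and alpha = 9.2%. The corrected Chi-squared and Fisher figures below were calculated from beta-binomial arm totals at 200/300 patients.

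**4. Power of a patient-clustered test.** Divide the oocyte numbers by DE. At 200/300 there are 1600 and 2400 oocytes, and the pooled proportion is (400 + 720)/4000 = 0.28. The standard errors are 0.01449·√DE under the null and 0.01431·√DE under the alternative. At ICC 0.05: (0.05 − 1.96·0.01684)/0.01662 = 1.02, giving 85%.

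| Assumed ICC | DE | Alpha, Chi-squared | Alpha, corrected | Alpha, Fisher | Power 200/300 | Power 180/270* | Power 163/163 |
|---|---|---|---|---|---|---|---|
| 0.02 | 1.14 | 6.6% | 6.1% | 6.4% | 90% | 87% | 76% |
| 0.05 | 1.35 | 9.2% | 8.6% | 8.9% | 85% | 81% | 69% |
| 0.10 | 1.70 | 13.3% | 12.6% | 12.9% | 76% | 71% | 59% |
| 0.20 | 2.40 | 20.6% | 19.7% | 20.2% | 61% | 56% | 45% |

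*10% dropout, assumed.

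**5. Where 5% is crossed.** Uncorrected Chi-squared exceeds 5% at any positive ICC. The corrected test crosses at about 0.0055 (200/300) or 0.0067 (163/163), and Fisher at about 0.003 or 0.007. At ICC 0.01 all three exceed 5% at both sizes, but only slightly (5.3% to 5.8%).

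**6. Where power falls to 80%.**
- 163 per group: 1300/1250.7 = 1.039, so ICC = 0.039/7 = 0.0056 (0.0061 with 163·8 = 1304 oocytes).
- 200/300: √DE = 0.05/(1.96·0.01449 + 0.842·0.01431) = 1.236, so DE = 1.528 and ICC = 0.528/7 = 0.075.
- 180/270: DE = 0.9·1.528 = 1.376, so ICC = 0.376/7 = 0.054.

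**7. Unequal oocyte numbers.** With an assumed mean of 8, minimum 4 and SD 3.5 (CV about 0.44), DE is about 1 + [8·(1 + 0.44²) − 1]·ICC, or 1 + 8.5·ICC. The 80% limits become 0.528/8.5 = 0.062 and 0.376/8.5 = 0.044.

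**8. Patient-level tests.** In simulation with ICC from 0 to 0.20 and at both sizes, error rates were 4.8–5.3% for a t-test on per-patient proportions, 4.9–5.3% for a cluster-robust ratio and 4.2–5.4% for the Wilcoxon test.

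**The case against.** The strongest reply is that the plan never says the blastocyst comparison will be an oocyte-level test. Two of its four listed tests are valid when applied to per-patient proportions, so what the text establishes is an unspecified unit, not an invalid test. That stands: the inflated error rate is conditional on the oocyte-level reading. But the choice of unit changes the p-value, and nothing in the plan excludes the reading its denominator suggests.

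The ICC is assumed, and the results run from about 6% to 21%. That also stands. The direction is firm; the size is not. An ICC of 0.01 is a level by which every listed test is above 5%, not a sharp threshold, and the excess there is negligible.

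Power is not shown to be inadequate, because recruitment is 200/300 and not 163 per group. I agree; only the sample-size sentence itself fails.

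Blastocyst proportion is not a named primary endpoint, and Section 3.1 describes data collection. This limits the severity, but the synopsis states a comparative purpose.

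Finally, clustering methods correct the variance, not bias from exclusions that may differ by arm (fewer than four 2PN embryos, no free MIRI-TL slot, incomplete annotation). Nor do a per-patient mean and a pooled ratio estimate the same quantity if oocyte yield is related to development. Both points are right, and both are separate from this one: a patient-level test holds its level for a given analysed set.

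**Conclusion.** The concern holds. Patients are randomised, the 1300 oocytes per group come from an independence formula, and no unit of analysis or clustering method is named. If the comparison is run on oocytes, the two-sided error rate exceeds 0.05 under any non-negligible ICC: modestly at 0.02 (6.1–6.6%), materially at 0.05 (8.6–9.2%) and at 0.10 (12.6–13.3%). These figures assume 8 oocytes per patient and an ICC the documents do not supply; unequal oocyte numbers make the problem somewhat worse. Loss of power at the planned 200/300 is possible but not shown. The claim of 80% power at about 163 patients per group is true only for an ICC near zero. This should be corrected before the data are analysed.

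**What to change.** In Section 7, state that the patient is the unit or cluster for the blastocyst comparison, and name one test. Suitable choices are GEE logistic regression clustered on patient, a cluster-robust ratio of blastocysts to inseminated oocytes, or the already listed t-test or Wilcoxon test on per-patient proportions. The choice should also say whether patients or oocytes carry equal weight.

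Restate the sample-size sentence with DE = 1 + (8 − 1)·ICC, note that unequal oocyte numbers make it slightly larger, and report power at 200 against 300 patients over a range of ICC.

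The cost is one or two sentences and a few lines of analysis code. Section 8.1 already records the number of eggs inseminated, so validity needs no new data and no extra patients; whether 200/300 also gives 80% power depends on the ICC. The price is a less favourable stated power. The unweighted per-patient t-test is simplest but gives up some power when oocyte numbers vary and the ICC is low: 86% against 90% for the cluster-robust ratio, simulated at ICC 0.02 and 200/300 with the unequal numbers assumed above.

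### The euploid-versus-aneuploid tSB comparison that sizes the MIRI-TL arm is observational but is tested without adjustment; an age-adjusted mixed model should be prespecified beside the unadjusted result

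*Combined protocol and SAP*

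**What the plan says.** Section 7 contains two sample-size calculations. The first compares blastocyst proportions between the randomised arms and needs about 163 patients per group. The second lies wholly within the MIRI-TL arm and compares tSB by ploidy, taking mean tSB as "96h with a variance of 49h in euploid embryos, and 98h (variance 49h) in aneuploid embryos". From this it concludes that "405 blastocysts (1620 inseminated oocytes = 203 patients) in the MIRI-TL group will need to be biopsied". It then allows for uptake of genetic screening: "Since ~80% of all patients receive PGS at our clinical site, we will need ~255 patients in our MIRI-TL group". This is the larger requirement for that arm, and the recruitment target is 300.

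The analysis text in the same section is generic: "Continuous data following a normal distribution will be analyzed with Students t-test", and otherwise data are "analyzed with non-parametric tests such as the Wilcoxon rank-sum test". The documents contain no regression model, covariate, stratification or within-patient analysis.

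Three other places matter:
- Section 8.0 randomises patients to incubator type only.
- Section 8.4 makes screening optional, so ploidy is known only where physician and patient had already chosen it.
- Section 3.2 lists "To collect enrollment data: demographics, IVF and pregnancy history". The synopsis sets a minimum age of 18 with no upper limit and admits frozen oocytes. Age is not named as a data field or as an analysis covariate.

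**The concern.** Ploidy is an observed embryo trait. Randomising patients to an incubator does nothing to balance euploid and aneuploid blastocysts within one arm. If a patient characteristic is related both to the chance of aneuploidy and to developmental speed, its effect is mixed into the ploidy difference. Maternal age is a natural candidate because it varies between patients and has no upper limit here.

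The target is small, 2 h against an SD of 7 h, so a shift of a fraction of an hour to an hour is large relative to the standard error. Depending on its direction, such a shift could raise the chance of declaring a ploidy marker that partly reflects the patient, or hide a real difference.

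Clustering is a related but separate issue. About two blastocysts per patient are counted as independent. Correcting only the standard errors for that would leave the confounding in place.

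**Working it through.** **Inputs from Section 7.** Difference 98 − 96 = 2 h; SD = √49 = 7 h; 80% power; two-sided 5% level; 405 biopsied blastocysts; blastocyst rate 25% ("25% of all inseminated oocytes would develop into blastocysts"); 1620/203 ≈ 8 oocytes per patient; screening uptake 80%. The euploid:aneuploid split is not stated; 1:1 is assumed below.

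**Reproducing the plan's figure.** For a two-sample comparison, n per group = 2(1.96 + 0.8416)² × 49 / 2² = 192.3, so 193 per group and 386 in total (388 with the t distribution). Two standard variants reach the stated 405:
- Dividing by the Wilcoxon efficiency 3/π gives 404 to 406.
- A 40:60 ploidy split gives 403.

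The rest follows: 405/0.25 = 1620 oocytes; 1620/8 = 202.5 patients; 203/0.80 ≈ 254, against about 255 stated. The figure is therefore an unadjusted two-sample calculation on independent blastocysts.

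**Sensitivity to a confounding shift.** SE = 7 × √(2/202.5) = 0.696 h. For a shift of b hours and no true ploidy effect, the rejection probability is 1 − Φ(1.96 − b/SE) + Φ(−1.96 − b/SE). For power, b is replaced by 2 + b.

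| Shift b (h) | Rejection, true effect 0 | Power, true effect 2 h |
|---|---|---|
| −1.0 | 30% | 30% |
| −0.5 | 11% | 58% |
| 0 | 5% | 82% |
| 0.5 | 11% | 95% |
| 1.0 | 30% | 99% |

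**What produces such a shift.** To first order, b = (tSB slope per year of age) × (mean age difference between ploidy groups). Neither term is in the documents, so these values are assumptions:
- 0 h/year gives b = 0 and 5% rejection.
- 0.1 h/year × 2 years = 0.2 h gives 6%.
- 0.3 h/year × 3 years = 0.9 h gives 25%.

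**Simulation check, all slopes assumed.** Settings: 203 patients, two blastocysts each, intraclass correlation 0.2, age SD 4 years, no true ploidy effect.
- With tSB slopes of 0.1 to 0.3 h/year crossed with aneuploidy log-odds slopes of 0.1 to 0.3 per year, the unadjusted bias runs from about 0.15 to 1.1 h. Rejection runs from about 5–7% in the lowest corner to about 36% in the highest.
- With a zero tSB slope, bias is about 0 and rejection is 4.7% to 5.6%.
- At 0.05 h/year, bias is 0.05 to 0.18 h and rejection 5.5% to 6.0%.
- With age in the model, bias stays within 0.05 h of zero.
- In the highest corner, cluster-robust standard errors without age still reject 34.6% of the time, against 35.8% for the t-test.

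**Cost of adjusting.** If age explains a share R² of the variance in ploidy, the need is about 405/(1 − R²) blastocysts. Each patient supplies on average 8 × 0.25 × 0.80 = 1.6 biopsied blastocysts.

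| R² (assumed) | Blastocysts | MIRI-TL patients |
|---|---|---|
| 0.05 | 427 | 267 |
| 0.10 | 450 | 282 |
| 0.15 | 477 | 298 |
| 0.20 | 507 | 317 |

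The planned 300 patients give 300 × 1.6 = 480 blastocysts before dropout, which covers R² up to 1 − 405/480 ≈ 0.156. Any fall in residual variance from including age would lower these needs.

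**The case against.** The strongest reply is that bias presupposes an estimand, and the plan states none. Section 3 aims to relate morphokinetic data to success, and Section 7 asks only whether tSB differs by ploidy. If tSB is meant purely as a marker, the marginal euploid-aneuploid difference is a legitimate target, and age adjustment answers another question: whether tSB adds information beyond age. This stands. It is a reason to keep the unadjusted result. It does not make that result sufficient for a claim that tSB marks ploidy independently of the patient.

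Second, a non-randomised contrast permits confounding but does not demonstrate it. This also stands: both age relations are absent from the documents, and with a zero or very small tSB slope the effect is negligible.

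Third, age is not a named field. It can be inferred from the demographics and the age criterion. Where frozen oocytes are used, however, age at enrolment may differ from age at retrieval, and nothing shows that the latter is captured.

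Fourth, the tSB contrast is not among the objectives in Sections 3.1 and 3.2. That is true, but it sets the larger of the two sample-size requirements for the MIRI-TL arm.

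**Conclusion.** The point holds as a possible bias of unknown size and direction in the comparison that sizes the MIRI-TL arm. The plan prespecifies nothing that could detect or remove it. At 405 blastocysts split 1:1, shifts of 0, 0.5 and 1.0 h give about 5%, 11% and 30% rejection under no ploidy effect. The same shifts in the opposing direction cut power for a true 2 h effect from 82% to 58% and 30%. The shifts are illustrations; only the 0.70 h standard error rests on the plan's figures, plus the assumed 1:1 split.

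A reader might infer more, and the documents do not support it:
- That the tSB result will be biased, or that the marker merely reflects age: no age association is given.
- That age could by itself account for the full 2 h: the largest average bias in the assumed scenarios is about 1.1 h, with both slopes at their highest values.
- That the unadjusted test is wrong and must go: it answers a legitimate marker question.

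The randomised blastocyst-rate comparison is not touched by this point. It is a low-cost improvement that should be made; it does not invalidate the design.

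**What to change.** In Section 7, for tSB by ploidy:
1. State the question: a marginal marker difference, a difference independent of patient characteristics, or both.
2. Prespecify a linear mixed model for tSB with ploidy as fixed effect, age at oocyte retrieval as covariate and a random intercept for patient. Report the adjusted difference in hours with its 95% CI beside the unadjusted difference.
3. Base any claim that tSB marks ploidy independently of the patient on the adjusted result.
4. As a sensitivity analysis, add the within-patient contrast in patients with both euploid and aneuploid blastocysts. It removes every fixed patient-level feature, measured or not, and needs no assumed slope. It uses fewer patients: with exactly two blastocysts each and an independent 1:1 split, about half (2 × 0.5 × 0.5) would contribute.
5. Confirm that age at retrieval is recorded, including when frozen oocytes are used.

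The cost is a few lines of analysis text, possibly one data field, and some precision. No extra patients are proposed. The planned 300 cover R² up to about 0.15 before dropout, and dropout would use part of that margin.
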